12.6. Reporting Serious or Unexpected AEs

Any SAE or serious suspected adverse reaction that occurs during the course of the study will be reported within 24 hours after the site becomes aware of the event.

All SAE reporting will adhere to the United States Code of Federal Regulations (CFR), specifically 21 CFR 312.32 for Investigational New Drugs, and applicable local regulations. The Investigator will notify the governing IRB or Ethics Committee of any SAEs and safety reports per IRB or Ethics Committee reporting requirements.

12.7. Follow-up of Adverse Events

All AEs (both serious and non-serious) should be followed until resolution or until a stable clinical endpoint is reached. All measures required for AE management and the ultimate outcome of the AE must be recorded in the source document and the eCRF.

Any SAE or serious suspected adverse reaction follow-up information requested should be provided in a timely manner. The additional information may include copies of hospital reports, autopsy reports, or other relevant documents.

13. STATISTICAL METHODS

13.1. Sample Size Determination

The trial size of 200 subjects (100 PUL-042 inhalation solution: 100 placebo) was chosen based on clinical considerations. The rates of infection to adequately estimate a sample size for a statistically significant result are unknown.

Enrolled subjects will be randomized with equal probability to receive blinded treatment consisting of either PUL-042 or placebo.

13.2. Subject Populations

Intent to Treat Population (ITT)

The ITT population will include all randomized subjects who receive at least one dose of experimental treatment (i.e., PUL-042 or Placebo)

The ITT population will be the primary data source used to address the primary study efficacy objectives

Modified Intention to Treat (MITT)

The MITT population will include all randomized subjects who receive at least one dose of experimental treatment (i.e., PUL-042 or Placebo) and are negative for SARS-CoV-2 infection at the time of administration of the first dose.

Safety Population

The Safety population is the ITT population defined as all randomized subjects who have received at least one dose of experimental treatment. The Safety population will be the data source used to evaluate the safety and tolerability of experimental treatment for this study.

13.3. Primary Objective

To determine the efficacy of PUL-042 Inhalation Solution in the prevention of viral infection with SARS-CoV-2 and progression to COVID-19 in subjects: 1) who have repeated exposure to individuals with SARS-COV-2 infection and 2) who are asymptomatic at enrollment.

The primary endpoint is the severity of COVID-19 as measured by the maximum difference from the baseline value in the Ordinal Scale for Clinical Improvement within 28 days from the start of experimental therapy. The Ordinal Scale for Clinical Improvement is a 9-point scale that measures disease severity at a given point in time. Notably, a score of 0 indicates that an individual is infection-free. The difference in scores obtained at different times provides a quantitative assessment of the incidence of infection and change in disease severity over that time interval. The change in severity between the placebo- and actively-treated groups will be analyzed by a linear statistical model adjusting for the main effect of randomized treatment and other relevant covariates (e.g., age, baseline OSCI Score, and presence of comorbidities). Because the statistical properties of these score differences might not conform to the theoretical requirements of this procedure, a Wilcoxon Rank-Sum (nonparametric) test may also be used to analyze the main effect of treatment. Full details of the planned analysis will be included in the Statistical Analysis Plan that will be developed for this study.

The Ordinal Scale for Clinical Improvement to be used in this study is derived from a draft scale proposed by the World Health Organization⁹ for clinical improvement as presented below in Table 4:

Descriptor	Score	
No clinical or virological evidence of infection	0	
Infected but no limitation of activities	1	
Limitation of activities	2	
Hospitalized not requiring oxygen therapy (SpO2 > 93% on room air)	3	
Oxygen by mask or nasal prongs	4	
Non-invasive ventilation or high-flow oxygen	5	
Intubation and mechanical ventilation	6	
Ventilation + additional organ support- pressors, RRT, ECMO	7	
Death	8	

Table 4:Ordinal Scale for Clinical Improvement (Derived from draft WHO scale)

It is possible that medically justified treatment and or procedures cannot be implemented due to the unavailability of equipment (e.g., scarcity of ventilators). In such cases, the data recorded in the eCRF should reflect the prescribed circumstances rather than the reality. For example, if clinical evaluation of a patient indicates the need for mechanical ventilation when no ventilator is available, that patient should be scored as 6 - "Intubation and mechanical ventilation" not as a lower score on the Ordinal Scale for Clinical Improvement.

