7.7. Schedule of Study Activities

The schedule of events is presented in Table 1.

Table 1:Schedule of Events

Event	Screening	Dose 1 ^a	Dose 2, 3, 4 ^a	Follow-up/Early Discontinuation from Study	Study Completion
	V1	V2	V3, 4, 5	V6	V7
	Day -2 to Day 1	Day 1 ^b	Days 3, 6, 10	Day 15	Day 29
Informed consent	X				
Medical history	Х				
Pregnancy test ^c	Х			Х	Х
Physical exam	Х	Х	Х	Х	
Vital signs ^d	Х	Х	Х	X	
Spirometry ^e	Х	Х	Х		
Symptom score ^f	Х	Х	Х	X	Х
SARS-CoV-2 test ^g		Х		X	Х
Study drug administration ^h		Х	Х		
Adverse events	Х	Х	Х	X	Х
Concomitant medications	Х	Х	Х	X	Х
Ordinal Scale for Clinical Improvement	X	Х	Х	Х	Х
Randomization	Х				

^a Vital signs, adverse events, and concomitant medications will be assessed prior to administration of study medication and also at 30 minutes post-dose.

^b There is no Day 0 in this study

^c Urine pregnancy test or serum pregnancy test if women are of child-bearing potential. If urine pregnancy test is positive, a serum pregnancy test must be done. Pregnancy test is required for Early Discontinuation, not Day 15.

^d Vital signs will include body temperature, blood pressure measurements, heart rate, and respiratory rate.

^e Spirometry will be done at screening to document eligibility. On days of dosing, spirometry will be done pre-dose and at 30 minutes (± 15) minutes post-dose. If the FEV1 is reduced > 10% compared to the pre-dose baseline the FEV1 should be repeated as clinically indicated

^fSARS-CoV-2 symptoms will be assessed at each visit according to the Symptom Score

^g SARS-CoV-2 testing will be performed pre-dose on Day 1 (Visit 2), Day 15 (Visit 6) and at Day 29 (Visit 7). Additional testing should be conducted at any point during the study when clinical symptoms are suggestive of potential COVID-19.

^h Study drug administration must be done by a health care professional

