7.11. Study Days 3, 6, and 10 (Study Drug Administration)

All procedures should occur ±1 day from the scheduled Study Day.

7.11.1. **Pre-dose**

On Days 3, 6, and 10 the following dosing guideline should be observed prior to dose administration:

• At Investigator discretion, dosing can be HELD or STOPPED at any time for safety reasons.

The following should be obtained prior to dosing.

- Physical examination
- Vital signs
- Spirometry
- Adverse event assessment
- Concomitant medication assessment
- SARS- CoV-2 infection symptom score
- Ordinal Scale for Clinical Improvement

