7.12. Study Day 15 (Follow-up)

Assessments should occur within +1 day of target Study Day.

The following assessments will be conducted:

- Physical examination
- Vital signs
- Nasaopharyngeal or oropharyngeal sample for SARS-CoV-2 testing
- Adverse event assessment
- Concomitant medication assessment
- SARS- CoV-2 infection symptom score
- Ordinal Scale for Clinical Improvement

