7.13. Early Discontinuation from Dosing and Study Withdrawal

Subjects who have received at least one dose of investigational treatment and are discontinued from dosing should continue to the final assessment at Day 29 according to the schedule of events specified for pre-dose assessments. There will be no post-dose assessments for these subjects.

Should the subject's study participation end prior to the completion of Study Day 15, the following assessments will be conducted as soon as possible after the decision to withdraw from the study is made.

- Physical examination
- Vital signs
- Serum pregnancy test or urine test (if urine test is positive, a serum test must be conducted)
- Nasaopharyngeal or oropharyngeal sample for SARS-CoV-2 testing
- Adverse event assessment
- Concomitant medication assessment

- SARS- CoV-2 infection symptom score
- Ordinal Scale for Clinical Improvement

7.14. Study Completion Day 29

Assessments should occur within +2 days of target Study Day.

- Serum pregnancy test or urine test (if urine test is positive, a serum test must be conducted)
- SARS- CoV-2 Symptom Score
- Adverse event assessment
- Concomitant medication assessment
- Ordinal Scale for Clincal Improvement
- Nasaopharyngeal or oropharyngeal sample for SARS-CoV-2 testing

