12. ADVERSE EVENTS

Adverse events will be described and graded according to the Toxicity Grading Scale for Healthy Adult and Adolescent Volunteers Enrolled in Preventive Vaccine Clinical Trials.

Symptoms and events associated with SARS-CoV-2 infection will be scored as per the SARS-CoV-2 infection symptom score (Table 2) and the Ordinal Scale for Clinical Improvement (Table 4). These findings should not be reported as Adverse Events.

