2.2 Endpoints

2.2.1 Primary Efficacy Endpoint

The primary endpoint is the severity of COVID-19 as measured by the maximum difference from the baseline value in the Ordinal Scale for Clinical Improvement within 28 days from the start of experimental therapy.

CONFIDENTIAL

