11. APPENDIX

11.1 Appendix A: Schedule of Events

Event	Screening	Dose 1ª	Dose 2, 3, 4 ª	Follow-up/Early Discontinuation from Study	Study Completion
	Vl	V2	V3, 4, 5	V6	V 7
	Day -2 to Day 1	Day 1 ^b	Days 3, 6, 10	Day 15	Day 29
Informed consent	Х				
Medical history	Х				
Pregnancy test ^c	X			Х	Х
Physical exam	Х	X	Х	Х	
Vital signs ^d	Х	Х	Х	Х	
Spirometry ^e	Х	X	X		
Symptom score ^f	Х	Х	Х	X	Х
SARS-CoV-2 test ^g		Х		Х	х
Study drug administrationh		X	Х		
Adverse events	Х	Х	Х	Х	Х
Concomitant medications	X	X	Х	Х	Х
Ordinal Scale for Clinical Improvement	x	Х	Х	x	Х
Randomization	X				

^a Vital signs, adverse events, and concomitant medications will be assessed prior to administration of study medication and also at 30 minutes post-dose.

^b There is no Day 0 in this study

^c Urine pregnancy test or serum pregnancy test if women are of child-bearing potential. If urine pregnancy test is positive, a serum pregnancy test must be done. Pregnancy test is required for Early Discontinuation, not Day 15.

d Vital signs will include body temperature, blood pressure measurements, heart rate, and respiratory rate.

^e Spirometry will be done at screening to document eligibility. On days of dosing, spirometry will be done pre-dose and at 30 minutes (±15) minutes post-dose. If the FEV1 is reduced > 10% compared to the pre-dose baseline the FEV1 should be repeated as clinically indicated

f SARS-CoV-2 symptoms will be assessed at each visit according to the Symptom Score

^g SARS-CoV-2 testing will be performed pre-dose on Day 1 (Visit 2), Day 15 (Visit 6) and at Day 29 (Visit 7). Additional testing should be conducted at any point during the study when clinical symptoms are suggestive of potential COVID-19.

^h Study drug administration must be done by a health care professional

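### Nothing ensures that a peak in the Ordinal Scale that resolves between visits enters the 28-day maximum, and the last gap between visits is 14 days

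*Protocol*

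**What the plan says.** **Endpoint.** SAP 2.2.1 and 6.1 and Protocol 6.1 and 13.3 all define the primary outcome as the "maximum difference from the baseline value in the Ordinal Scale for Clinical Improvement within 28 days from the start of experimental therapy".

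**What each score measures.** Protocol 13.3, repeated in SAP 6.1: "The Ordinal Scale for Clinical Improvement is a 9-point scale that measures disease severity at a given point in time". No look-back period is attached to the score.

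**When it is scored.** Protocol Table 1 and SAP Appendix A list Screening, Day 1, Days 3, 6 and 10, Day 15 and Day 29. The dosing visits have a window of ±1 day. For Day 15, "Assessments should occur within +1 day of target Study Day" (Protocol 7.12). For Day 29, "Assessments should occur within +2 days of target Study Day" (Protocol 7.14).

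**Contact between visits.** Table 1, note g: "Additional testing should be conducted at any point during the study when clinical symptoms are suggestive of potential COVID-19". This asks for a swab and does not mention an OSCI score. SAP 4 leaves unscheduled visits out of the summaries and lists them only. SAP 4.3 summarises by nominal visit.

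**Other records.** Protocol 12 and 12.4 send COVID-19 symptoms and events to the symptom score and the OSCI, and add: "These findings should not be reported as Adverse Events". SAP 6.2 uses eCRF dates for ICU stay and mechanical ventilation, and vital status for death. Protocol 10 has procedures documented and medications recorded with start and stop dates. SAP 5.6 says procedures are free text and only listed.

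**The concern.** A maximum over 28 days needs either continuous observation or a question about what happened between observations. The plan provides for neither. As scheduled, the recorded maximum is the worst status on five post-dose days, and half of follow-up lies between the last two of them.

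Take a subject who falls ill on Day 17, is in hospital on oxygen (score 4) on Days 20 to 25, and is home without limitation by Day 29. The Day 29 score is 0 or 1. Unless some other record is brought in, the primary outcome for that subject is a change of 0 or 1 instead of 4.

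At stake are the levels between mild infection and intubation: limitation of activities (2), hospitalisation (3), oxygen (4), and non-invasive ventilation or high-flow oxygen (5). Losing some of them lowers recorded severity in both arms and shrinks a real difference between them.

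**Working it through.** The documents give no capture rate, peak duration or power for this endpoint, so there is no planned figure to reproduce. Durations and onset patterns below are assumptions.

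**Gaps.** Visits on Days 1, 3, 6, 10, 15 and 29 give gaps of 2, 3, 4, 5 and 14 days, 28 in total. The last gap is 14/28 = 50% of follow-up. With the +1 and +2 day windows it can run from 13 days (Day 16 to Day 29) to 16 days (Day 15 to Day 31).

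**Uniform onset.** A peak lasting L days falls wholly inside a gap g if it starts in the first g − L days of that gap. Missed share = Σ max(0, g − L) / 28.

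- L = 3: (0 + 0 + 1 + 2 + 11)/28 = 14/28 = 50%
- L = 5: 9/28 = 32%
- L = 7: 7/28 = 25%
- L = 10: 4/28 = 14%

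For L of 5 days or more, every missed peak lies between Days 15 and 29. Among peaks starting in that gap, the missed share is (14 − L)/14: 79%, 64%, 50% and 29%.

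**Front-loaded onset.** Let onset be exponential with mean 7 days from Day 1. A gap from a to b days after Day 1, longer than L, contributes exp(−a/7) − exp(−(b − L)/7).

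- L = 3: 0.065 (Days 6 to 10) + 0.069 (Days 10 to 15) + 0.107 (Days 15 to 29) = 0.241
- L = 5: exp(−14/7) − exp(−23/7) = 0.098
- L = 7: exp(−14/7) − exp(−21/7) = 0.086
- L = 10: exp(−14/7) − exp(−18/7) = 0.059

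That is about 24%, 10%, 9% and 6%. Restricting onset to the 28 days divides each by 1 − exp(−4) = 0.982, which changes them by less than one percentage point.

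**Day 15 maximum.** Over the first four gaps with uniform onset, the missed share is 3/14 = 21% for L = 3 and zero for L of 5 or more. The problem belongs mainly to the Day 29 maximum.

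**Illustrative effect on power.** Suppose 20% of placebo and 10% of active subjects have a peak event, with 100 per arm, two-sided 0.10 and the normal approximation. Power = Φ((d − 1.645·se0)/se1), where se0 is the pooled and se1 the unpooled standard error.

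- Full capture: se0 = √(0.15 × 0.85 × 0.02) = 0.0505 and se1 = √((0.16 + 0.09)/100) = 0.050, so Φ((0.10 − 0.083)/0.050) = 63%
- 75% capture (15% against 7.5%): 51%
- 50% capture (10% against 5%): 38%

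These rates are not in the documents, and a two-proportion test is not the planned ANCOVA. The figures show direction and rough scale only.

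**The case against.** A reader might infer that peaks between visits are never recorded. The documents do not support that. ICU stay and ventilation carry dates, and death is recorded as vital status. Oxygen or non-invasive ventilation may appear among the procedures. Protocol 12 says COVID-19 events will be scored on the OSCI without restricting this to visits, and Protocol 13.3 tells sites how to score a patient who needs a ventilator when none is available. The eCRF has not been seen. All this stands. But Protocol 12 sets no timing, field or derivation, procedures are free text, and SAP 6.1 brings none of these sources into the maximum.

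A reader might also extend the point to the symptom score, since "SARS-CoV-2 symptoms will be assessed at each visit according to the Symptom Score". That does not follow. SAP 6.2 plans no maximum for symptoms and compares them visit by visit, and fever is graded from the temperature taken with vital signs, which an interview cannot reliably recover.

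A third inference would be that the comparison is invalid. Both blinded arms follow one schedule, so the null test holds.

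The uniform-onset shares are also a stress case. Protocol 7.2.1 enrols after recent exposure, so earlier onset is plausible, and a missed peak may still leave a lower nonzero score at the next visit. Finally, the trial seeks preliminary data and makes no power claim (Protocol 5 and 13.1; SAP 4.5), which lowers the urgency.

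**Conclusion.** The point holds in this form: a 28-day maximum is built from point-in-time scores on five post-dose days, and no provision ensures that peaks resolving between visits enter it. The exposed range is mainly scores 2 to 5.

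Depending on peak duration (3 to 10 days), the share of peaks with no visit is 14% to 50% under uniform onset and about 6% to 24% under front-loaded onset. Duration and onset are both assumed. The consequence is under-recorded severity in both arms and reduced sensitivity. Bias follows only if treatment changes when illness occurs or how long it lasts, because capture would then differ by arm. This should be fixed, because detail not collected during the trial may not be recoverable afterwards. It does not invalidate the trial.

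**What to change.** **Protocol 8.2 and Table 1.** At each post-baseline visit, record two OSCI values: status on that day, and worst status since the previous visit, taken from interview and available records. Add start and stop dates for each level of 2 or above.

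**SAP 6.1 and 6.2.** Derive the Day 15 and Day 29 maxima from the worst-since-last-visit values dated within the period, any unscheduled OSCI scores, and the dated ventilation and death records. The scale has no ICU level, so an ICU stay alone does not fix a score. Keep day-of-visit values for the by-visit tables and plots. The dates also settle what counts when the last visit falls on Day 30 or 31. Leave the symptom score unchanged.

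**Cost.** A few extra eCRF fields and short additions to both documents, with no new visit or test. The real downside is recall error over up to 14 days at the Day 29 visit (slightly longer if that visit is late). It should be smaller for hospitalisation and oxygen, where records can be checked, than for limitation of activities.

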13.4. Secondary Objectives

To determine the difference in incidence of SARS-CoV-2 infection 28 days from the start of experimental therapy in subjects who test negative for SARS-CoV-2 at the pre-treatment visit

To determine the difference in incidence of SARS-CoV-2 infection 14 days from the start of experimental therapy in subjects who test negative for SARS-CoV-2 at the pre-treatment visit (MITT)

To compare the severity of COVID-19 within 14 days from the start of experimental therapy (ITT)

To compare the severity of COVID-19 within 28 days from the start of experimental therapy (ITT)

To assess the requirement for ICU admission within 28 days from the start of experimental therapy (ITT)

To assess the requirement for mechanical ventilation within 28 days from the start of experimental therapy (ITT)

To assess mortality within 28 days from the start of experimental therapy (ITT)

To determine the tolerability of PUL-042 Inhalation Solution in this population (ITT population)

13.5. Safety Analysis

A comprehensive statistical analysis plan (SAP) will be finalized prior to unblinding of the study results. The SAP may modify the plans outlined in the protocol; however, any major modifications of planned analyses will be reflected in a protocol amendment. Safety data will be presented in tabular and/or graphical format and summarized descriptively, if appropriate.

Adverse events will be described and graded according to the Toxicity Grading Scale for Healthy Adult and Adolescent Volunteers Enrolled in Preventive Vaccine Clinical Trials.

Treatment-emergent AEs, vital signs, physical examinations, clinical laboratory data, lung function tests, and noncompliance will be reviewed on an ongoing basis during the study to evaluate the safety of the subjects.

14. ADMINISTRATION OF THE STUDY

14.1. Regulatory Considerations

This study will be conducted in compliance with the protocol, International Conference on Harmonisation (ICH) Good Clinical Practice (GCP) Guidelines, and the applicable local regulatory requirements. This study will be conducted in accordance with the ethical principles that originate in the Declaration of Helsinki and ICH Guidelines for GCP.

Study protocols and informed consent forms will be approved by the appropriate IRB or Ethics Committee prior to initiation of the study. All subjects will sign an informed consent form prior to any study-specific procedures. The study will be monitored for regulatory and protocol compliance by a study monitor selected by Pulmotect.

14.2. Institutional Review Board (IRB)/Ethics Committee

The Investigator must submit the final protocol and proposed informed consent document to an IRB/ethics committee that complies with the ICH GCP. The IRB/ethics committee will provide the Investigator with a written decision regarding the conduct of the study and a copy of the document will be forwarded to the Sponsor. The study will not be initiated and subjects will not be enrolled until the appropriate documentation of IRB/ethics committee approval of the study protocol and the informed consent form has been received.

Substantive modifications to the protocol must be submitted to the IRB/ethics committee for approval. Administrative changes to the protocol, such as revisions for clarification that do not affect the conduct of the study or increase the risk to the subject, should be submitted to the IRB/ethics committee for informational purposes; formal approval is not required.

The Investigator must also submit any written information that will be given to the study subjects, as well any subject recruitment material, to the IRB/ethics committee for approval prior to use.

The Investigator will make appropriate and timely reports to the IRB/ethics committee as required by applicable government regulations and IRB/ethics committee policy. In addition to progress reports, all known information regarding SAEs will be reported per IRB/ethics committee requirements.

It is the Investigator's obligation to provide the Sponsor with copies of all study-related correspondence with the IRB/ethics committee in a timely fashion and to retain the originals as part of the Site Regulatory File. The Site Regulatory File will be made available as requested for monitoring or quality assurance review during site audits and to governmental regulatory representatives as required.

